13.3. Update to Study Sample Size Due to COVID-19 Pandemic

According to the study protocol version 9.01 dated 29 July 2019, 160 patients were to be enrolled into the study according to the defined age group distribution. Prior to the outbreak of COVID-19 pandemic and until March 2020, 145 patients were enrolled into the study.

The COVID-19 pandemic significantly affected all study sites' ability to enroll additional patients. There was a great uncertainty regarding when restrictions would be lifted and study sites would be able to resume enrollment. Therefore, MediWound explored whether the recruitment to the study can be completed at this stage, with 145/160 (91%) of patients

enrolled, in line with FDA guidance document: "Statistical Considerations for Clinical Trials During the COVID-19 Public Health Emergency", issued on 17 June 2020.

The original sample size and statistical power calculations for this study were based on effects reached during the first Phase 3 study (MW2004-11-02) which was completed in 2009. Since then MediWound had also completed the recruitment and the 12 month follow up of 175 adult patients randomized to the Phase 3 study MW2010-03-02 (DETECT). Power calculations were performed also using data from this latest phase 3 study.

The updated sample size calculations, presented below, confirmed that based on a sample size of 145 patients, the study is sufficiently powered to meet the primary and main secondary and safety endpoints as originally planned. Thus, the study provides all required data to evaluate NexoBrid's safety and efficacy in pediatric patients while enabling the early availability of the product to address an unmet need in the pediatric population. These power calculations were submitted to the pediatric committee (PDCO) within the EMA and to the FDA to support MediWound's request for early completion of enrollment.

The request for early study completion was endorsed by the study's DSMB, relying on the confirmation that study endpoints can be met with the sample size of 145 patients and pending FDA and EMA approval.

The request for early completion of enrollment was accepted by both the FDA and the PDCO (EMA) and therefore the enrollment of patients into the study was completed with a total of 145 patients, with the following age distribution:

- 45 patients ≥0 months and ≤23 months old
- 30 patients ≥24 months and ≤3 years old
- 50 patients ≥4 years and ≤11 years old
- 20 patients ≥12 years and <18 years old

Power calculations for MW2012-01-01 study considering a reduced sample size of 145 patients

Sample sizes needed to achieve a power of 90% for the statistical tests in the analysis of MW2012-01-01 (CIDS) are estimated. The calculations are based on the 12 months' data of

the DETECT study (MW2010-03-02), as well as on data from the previous study MW2004-11-02.

Note, that the power calculated for each test does only refer to the power of that specific test. When conducting multiple tests in a hierarchical testing procedure, endpoints which are positioned at later points of the hierarchy, might not be tested if earlier tests do not reject the corresponding null hypotheses. Therefore, the power of the tests in a hierarchical testing procedure also depends on the other endpoints and will be lower.

Time to Complete Eschar Removal

Estimate based on study MW2004-11-02

The sample size calculation based on the results of study MW2004-11-02 assumes that the proportional hazards assumption will be judged appropriate and consequently a Cox model will be used for the primary analysis:

Estimated log hazard ratio from study MW2004-11-02 (NexoBrid versus SoC) = -1.39, using a Cox proportional hazards model with treatment as only covariate.

Standard error = 0.28

Target log hazard ratio = -1.39 + 0.28/2 = -1.25; target hazard ratio λ = 0.29.

The formula for total number of events D is: $D = \frac{4(z_{\alpha} + z_{\beta})^2}{(\ln \lambda)^2}$

(Piantadosi, Clinical Trials: A Methodologic Perspective, p.169)

 $z_{\alpha} = 1.96$;

 z_{β} = 1.28 for 90% power.

If the proportion of events in group 1 is denoted by p1 = 0.59

and the proportion of events in group 2 is denoted by p2 = 0.70

which are the observed proportions in the study MW2004-11-02, the number of patients required per group is $n = \frac{2D}{p_1 + p_2} = 42$ (to the nearest even number), 21 in each group.

Estimate based on study MW2010-03-02

Since the proportional hazards assumption was rejected in study MW2010-03-02 trial, the sample size calculation based in this study assumes that this will also be the case in the CIDS study and consequently a generalized Wilcoxon-Gehan test will be used in the analysis. Based on the data from MW2010-03-02, simulations were conducted, using the generalized Wilcoxon-Gehan-Test for the primary analysis, resulting in a total sample size of 94 (47 per group) needed to achieve a power of 90%.

% Wound Area Surgically Excised for Eschar Removal

Estimate based on study MW2004-11-02

Estimated difference in mean percent wound excised from study MW2004-11-02 (NexoBrid vs. SoC) = 15.1 - 59.6 = -44.5.

Standard error = 5.3

Target difference $\Delta = -44.5 + 5.3/2 = -41.85$.

The formula for the number of patients per group n is: $n = \frac{2(z_{\alpha} + z_{\beta})^2 \, \sigma^2}{\Delta^2}$

where

 $z_{\alpha} = 1.96$;

 z_{β} = 1.28 for a power of 90%;

 σ = the estimated common standard deviation of percent area of wound excised = 34.

For 90% power, number per group = 14

Estimate based on study MW2010-03-02

Estimated mean % area surgically excised from study MW2010-03-02: NexoBrid 3.66; SoC 58.74

Standard errors: NexoBrid 2.09; SoC 5.78

Difference: -55.08; Standard error of difference = 5.89

Target difference Δ = -55.08 + 5.89/2 ≈ -52.13.

Using a two-sided two-sample t-test with a two-sided significance level of 5%, the total sample size required to achieve a power of 90% is 24 (12 per group).

Incidence of Surgical Excision

Estimate based on study MW2004-11-02

Estimated proportions having surgical excision from study MW2004-11-02: NexoBrid 0.42; SoC 0.80

Standard errors: NexoBrid 0.057; SoC 0.044

Difference = 0.38; Standard error of difference = 0.073

Anticipated difference: 0.38-0.073/2 ≈ 0.34

We therefore take the anticipated proportion with surgical excision to be: NexoBrid 0.44 and SoC 0.78.

Using Fisher's exact test with a two-sided significance level of 5%, the total sample size required to achieve a power of 90% is 96 (48 per group).

Estimate based on study MW2010-03-02

Estimated proportions having surgical excision from study MW2010-03-02: NexoBrid 0.04; SoC 0.72

Standard errors: NexoBrid 0.023; SOC 0.052

Difference = 0.68: Standard error of difference = 0.057

Anticipated difference: $0.68-0.057/2 \approx 0.652$

We therefore take the anticipated proportion with surgical excision to be: NexoBrid 0.05 and SOC 0.70.

Using Fisher's exact test with a two-sided significance level of 5%, the total sample size required to achieve a power of 90% is 26 (13 per group).

Incidence of Autograft in DPT Wounds (wound level analysis)

Estimate based on study MW2004-11-02

Only subjects with at least one DPT target wound will be eligible for this analysis. The expected proportion of subjects with at least one DPT target wound estimated from study MW2004-11-

02 is 62.6%.

Estimated log OR using GEE approach from study MW2004-11-02 (NexoBrid vs SoC): -0.676

Standard Error: 0.40

Anticipated log OR: -0.676+0.40/2=-0.476

Using the normal approximation to the Wald test statistics (see for example Shih (1997)) we obtain that a total sample size of 1150 patients (720 evaluable) is needed to achieve a power of 90% using a two-sided significance level of 5%. This means that a sample size of 575 subjects per arm would be required to obtain the minimum number of evaluable subjects for

90% power in this endpoint.

Estimate based on study MW2010-03-02

Only subjects with at least one DPT target wound will be eligible for this analysis. The expected proportion of subjects with at least one DPT target wound estimated from study MW2010-03-02 is 58%.

Estimated log OR using GEE approach from study MW2010-03-02 (NexoBrid vs SoC): -0.5078

Standard Error: 0.4988

Anticipated log OR: -0.5078+0.4988/2=-0.5078

Using the normal approximation to the Wald test statistics (see for example Shih (1997)) we obtain that a total sample size of 5880 patients (3410 evaluable) is needed to achieve a power of 90% using a two-sided significance level of 5%. This means that a sample size of 2940 subjects per arm would be required to obtain the minimum number of evaluable subjects for 90% power in this endpoint.

Page 128 of 138

Area of Autograft in DPT Wounds (wound level analysis)

Estimate based on study MW2004-11-02

Only subjects with at least one DPT target wound will be eligible for this analysis. The expected proportion of subjects with at least one DPT target wound estimated from study MW2004-11-

02 is 62.6%.

Estimated difference in mean area Autograft in DPT wounds using GEE approach from study

MW2004-11-02 (NexoBrid vs SoC): -11.41

Standard Error: 4.89

Anticipated difference: -11.41+4.89/2=-8.97

Using the normal approximation to the Wald test statistics (see for example Shih (1997)) we obtain that a total sample size of 486 patients (304 evaluable) is needed to achieve a power of 90% using a two-sided significance level of 5%. This means that a sample size of 243 subjects per arm would be required to obtain the minimum number of evaluable subjects for

90% power in this endpoint.

Estimate based on study MW2010-03-02

Only subjects with at least one DPT target wound will be eligible for this analysis. The expected proportion of subjects with at least one DPT target wound estimated from study MW2010-03-

02 is 58%.

Estimated difference in mean area Autograft in DPT wounds using GEE approach from study

MW2010-03-02 (NexoBrid vs SoC): -9.39

Standard Error: 6.28

Anticipated difference: -9.39+6.28/2=-6.25

Using the normal approximation to the Wald test statistics (see for example Shih (1997)) we obtain that a total sample size of 1590 patients (922 evaluable) is needed to achieve a power of 90% using a two-sided significance level of 5%. This means that a sample size of 795 subjects per arm would be required to obtain the minimum number of evaluable subjects for

90% power in this endpoint.

Blood Loss

Estimate based on study MW2004-11-02

Estimated mean blood loss from study MW2004-11-02: NexoBrid 421.93 ml; SoC 1024.27 ml

Standard errors: NexoBrid 129.52; SoC 240.98

Difference: -602.33; Standard error of difference: 273.58

Anticipated difference: -602.33 + 267.75 / 2 = -468.47

Using a two-sided two-sample t-test with a two-sided significance level of 5%, the total number of evaluable patients needed to achieve a power of 90% is 346 (173 per group). Incorporating a rate of missing values of 30%, a total of 494 patients (247 per group) needs to be enrolled to achieve a power of 90%.

Estimate based on study MW2010-03-02

Note: In the MW2010-03-02 study, a different formula for the calculation of blood loss, than will be applied to the CIDS study, was used. However, both formulas try to estimate the same quantity and are therefore considered comparable.

Estimated mean blood loss from study MW2010-03-02: NexoBrid 14.17 ml; SoC 814.51 ml

Standard errors: NexoBrid 66.15; SOC 167.74

Difference: -800.34; Standard error of difference: 156.08

Anticipated difference: -800.34 + 156.08 / 2 = -722.30

Using a two-sided two-sample t-test with a two-sided significance level of 5%, the total number of evaluable patients needed to achieve a power of 90% is 56 (28 per group). Incorporating a rate of missing values of 30%, a total of 80 patients (40 per group) needs to be enrolled to achieve a power of 90%.

Time to Complete Wound Closure

In the following, a non-inferiority margin of 7 days is already implemented by adding 7 days to the wound closure times of the SoC group.

Estimate based on study MW2004-11-02

Estimated log hazard ratio from study MW2004-11-02 (NexoBrid versus SoC) = 0.49, using a Cox proportional hazards model with shared frailty adjusted for center, age, %TBSA area of the wound and number of TWs $(1,2,3-4, \ge 5)$.

Standard error = 0.63

Target log hazard ratio = 0.49 - 0.63/2 = 0.18; target hazard ratio $\lambda = 1.2$.

The formula for total number of events D is: $D = \frac{4(z_{\alpha} + z_{\beta})^2}{(\ln \lambda)^2}$

(Piantadosi, Clinical Trials: A Methodologic Perspective, p.169)

 $z_{\alpha} = 1.96$;

 z_{β} = 1.28 for 90% power.

If the proportion of events in NexoBrid group is denoted by $p_1 = 0.64$

and the proportion of events in SoC group is denoted by $p_2 = 0.56$,

which are the observed proportions in the study MW2004-11-02, the number of subjects to be enrolled to achieve a power of 90% for the non-inferiority test is $n = \frac{2D}{p_1 + p_2} = 2164$ (1082 in each group).

Estimate based on study MW2010-03-02

Estimated log hazard ratio from study MW2010-03-02 (NexoBrid versus SoC) = 1.56, using a Cox proportional hazards model with shared frailty adjusted for center, age, %TBSA, proportion of the FT area of a patient and number of TWs (1,2,3-4, ≥5).

Standard error = 0.41

Target log hazard ratio = 1.56 - 0.41/2 = 1.36; target hazard ratio $\lambda = 3.90$.

The formula for total number of events D is: $D = \frac{4(z_{\alpha} + z_{\beta})^2}{(\ln \lambda)^2}$

(Piantadosi, Clinical Trials: A Methodologic Perspective, p.169)

 $z_{\alpha} = 1.96$;

 z_{β} = 1.28 for 90% power.

If the proportion of events in NexoBrid group is denoted by $p_1 = 0.62$

and the proportion of events in SoC group is denoted by $p_2 = 0.73$,

which are the observed proportions in the study MW2010-03-02, the number of subjects to be enrolled to achieve a power of 90% for the non-inferiority test is $n = \frac{2D}{p_1 + p_2} = 34$ (17 in each group).

Cosmesis and Function: MVSS at 12 months

Estimate based on study MW2004-11-02

Estimated difference in MVSS at 24 months from previous study (NexoBrid vs. SoC) = 3.32 - 3.83 = -0.51.

Standard error = 0.50

Target difference $\Delta = -0.51 + 0.50/2 = -0.26$.

The formula for the number of patients per group n is: $n = \frac{2(z_{\alpha} + z_{\beta})^2 \sigma^2}{q(\Delta - d_0)^2}$

where

 $z_{\alpha} = 1.96$;

 z_{β} = 1.28 for a power of 0.9;

 σ = the estimated common standard deviation= 2.33 (taken from previous study);

 d_0 = clinical equivalence level = 1.9;

q = proportion who are retained in follow-up to 12 months = 0.7 (assuming 30% loss to follow-up over 1 year)

For 90% overall power, the required sample size per group is 35 (70 overall).

Estimate based on study MW2010-03-02

Estimated mean MVSS at 12 months from study MW2010-03-02: NexoBrid 3.70; SoC 5.08

Standard errors: NexoBrid 0.24; SoC 0.38

Difference: -1.38; Standard error of difference: 0.44

Anticipated difference: -1.38 + 0.44 / 2 = -1.16

The non-inferiority margin employed for this analysis is 1.9 score points.

Using a one-sided two-sample t-test with a significance level of 2.5%, 36 evaluable subjects are needed (18 in each group) to achieve a power of 90%. Using a conservative rate of missing values of 30%, the total sample sizes needed to achieve a power of 90% in the analysis is 52 (26 per group).

Note: In the analysis missing data will be imputed, leading to more evaluable subjects, increasing the power.

Cosmesis and Function: MVSS at 24 months

Estimate based on study MW2004-11-02

Estimated difference in MVSS at 24 months from previous study (NexoBrid vs. SoC) = 3.32 - 3.83 = -0.51.

Standard error = 0.50

Target difference $\Delta = -0.51 + 0.50/2 = -0.26$.

The formula for the number of patients per group n is: $n = \frac{2(z_{\alpha} + z_{\beta})^2 \sigma^2}{q(\Delta - d_0)^2}$

where

 $z_{\alpha} = 1.96$;

 z_{β} = 1.28 for a power of 0.9;

 σ = the estimated common standard deviation= 2.33 (taken from previous study);

 d_0 = clinical equivalence level = 1.9;

q = proportion who are retained in follow-up to 24 months = 0.5 (assuming 50% loss to follow-up over 2 years)

For 90% overall power, the required sample size per group is 49 (98 overall).

Estimate based on study MW2010-03-02

Since at this time the 24 months MVSS data of the MW2010-03-02 study is not yet available, the 12 months data will be used for the calculation.

Estimated mean MVSS at 12 months from study MW2010-03-02: NexoBrid 3.70; SoC 5.08

Standard errors: NexoBrid 0.24; SoC 0.38

Difference: -1.38; Standard error of difference: 0.44

Anticipated difference: -1.38 + 0.44 / 2 = -1.16

The non-inferiority margin employed for this analysis is 1.9 score points.

Using a one-sided two-sample t-test with a significance level of 2.5%, 36 evaluable subjects are needed (18 in each group) to achieve a power of 90%. Using a conservative rate of missing values of 50%, the total sample sizes needed to achieve a power of 90% in the analysis is 72 (36 per group).

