9.1.1. Primary Endpoint: Time to Complete Eschar Removal

Estimated log hazard ratio from study MW2004-11-02 (SoC versus NexoBrid) = -1.39, using a Cox proportional hazards model with treatment as only covariate.

Standard error = 0.28

Target log hazard ratio = -1.39 + 0.28/2 = -1.25; target hazard ratio $\lambda = 0.29$.

The formula for the number of events D (successful complete eschar removals) is:

$$D = \frac{4(z_{\alpha} + z_{\beta})^2}{(\ln \lambda)^2}$$

(Piantadosi, Clinical Trials: A Methodologic Perspective, p.169)

 $z_{\alpha} = 1.96$;

 z_{β} = 1.28 for 90% power.

If the proportion of events in NexoBrid group is denoted by $p_1 = 0.59$

and the proportion of events in SoC group is denoted by $p_2 = 0.70$,

which are the observed proportions in the study MW2004-11-02, the number of patients required $n = \frac{2D}{p_1 + p_2} = 42$ (to the nearest even number), 21 in each group.

In accordance with the European regulatory requests and planned age distribution, we believe that a sample size of 80 patients per arm will detect with a 90% power a difference on the primary endpoint, which is well within what would be expected, based on the results from the previous study.

Based on the above calculations, we plan a study with total sample size of 160 patients; 80 (NexoBrid) + 80 (SoC)⁵.

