9.1.2. Secondary Endpoint: Incidence of Surgical Excision

Estimated proportions having surgical excision from study MW2004-11-02: NexoBrid 0.42; SoC 0.80

Standard errors: NexoBrid 0.057; SoC 0.044

Difference = 0.38; Standard error of difference = 0.073

Anticipated difference: 0.38-0.073/2 ≈ 0.34

We therefore take the anticipated proportion with surgical excision to be: NexoBrid 0.44 and SoC 0.78.

Using Fisher's exact test, the power achieved with a total sample size of 160 patients (80 in each group) using a two-sided significance level of 5% is 99.1%.

Statistical Analysis Plan V02 of 31 May 2021

⁵ Updated calculations were performed to support the final sample size of 145 patients enrolled into the study (provided in 13.3 13.3Update to Study Sample Size Due to COVID-19 Pandemic)

9.1.3. **Secondary Endpoint: Blood Loss**

Estimated mean blood loss from study MW2004-11-02: NexoBrid 421.93 ml; SoC 1024.27 ml

Standard errors: NexoBrid 129.52; SoC 240.98

Difference: -602.33; Standard error of difference: 273.58

Anticipated difference: -602.33 + 273.58 / 2 = -465.54

Using a two-sided two-sample t-test the power with a total sample size of 160 patients and a two-sided significance level of 5% is 58.8%.

Secondary Endpoint: Area of Autograft in DPT Wounds

The proportion of subjects with at least one DPT wound was 62.6% in the study MW2004-11-02. Therefore, if 160 patients are enrolled to the CIDS study, we expect 100 patients to have at least one DPT wound and be thereby eligible for this analysis.

Estimated difference in mean area autograft in DPT wounds from study MW2004-11-02 (NexoBrid vs. SoC) = 13.30-23.63 = -10.33.

Standard error = 6.02

Target difference $\Delta = -10.33 + 6.02/2 \approx -7.32$.

Using a two-sided two-sample t-test the power with a total sample size of 160 patients using a two-sided significance level of 5% is 23.1%.

Secondary Endpoint: Incidence of Autograft in DPT Wounds

Estimated log OR using GEE approach from study MW2004-11-02 (NexoBrid vs SoC): -0.676

Standard Error: 0.40

Anticipated log OR: -0.676+0.40/2=-0.476

Using the normal approximation to the Wald test statistics (see for example Shih (1997)) we obtain a power of 53.3% with a total sample size of 160 patients using a two-sided significance level of 5%.

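### The sample size for wound closure (34) and the power for blood loss (58.8%) follow from the SAP's formulas but are too favourable: the first ignores the variance of its own input, the second the planned missing data and the final N of 145

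*SAP*

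**What the plan says.** **Wound closure (SAP 13.3, estimate from MW2010-03-02).** The estimate is reported as "NexoBrid versus SoC) = 1.56, using a Cox proportional hazards model with shared frailty adjusted for center" and other covariates, with standard error 0.41. It is shrunk by half a standard error: "Target log hazard ratio = 1.56 - 0.41/2 = 1.36". The number of events is D = 4(zα + zβ)²/(ln λ)² with zα = 1.96 and zβ = "1.28 for 90% power". Dividing by the event proportions 0.62 and 0.73 gives 34 patients, 17 per group. The parallel estimate from MW2004-11-02 (log hazard ratio 0.49, standard error 0.63) gives 2164.

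**Eschar removal (SAP 9.1.1, repeated in 13.3).** "Target log hazard ratio = -1.39 + 0.28/2 = -1.25" goes into the same formula with event proportions 0.59 and 0.70, giving 42 patients. Section 13.3 adds a simulation from MW2010-03-02 with the Wilcoxon-Gehan test, giving 94.

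**Blood loss (SAP 9.1.3 and 13.3, MW2004-11-02).** Section 9.1.3 has "Anticipated difference: -602.33 + 273.58 / 2 = -465.54" and then "Using a two-sided two-sample t-test the power with a total sample size of 160 patients and a two-sided significance level of 5% is 58.8" per cent. No missing-data allowance is mentioned there. Section 13.3 restates the standard error of the difference as 273.58, halves 267.75 to reach −468.47, and reports that the number of evaluable patients "needed to achieve a power of 90% is 346 (173 per group"). It continues: "Incorporating a rate of missing values of 30%, a total of 494 patients".

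Section 13.3 presents these calculations as confirming that 145 patients are enough for the primary and the main secondary and safety endpoints. It says that they were submitted to the regulators in support of ending enrolment early.

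**The concern.** The event formula treats events as independent, so that the standard error of the log hazard ratio is 2/√D. The planned wound-closure analysis is at wound level with clustering within patients (SAP 11.1.5.1), and the input comes from a shared-frailty model. The SAP uses the reported standard error to shrink the effect and then drops it when computing variance. If that standard error is about twice what the formula implies, the required size is about four times larger.

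This matters because 34 is the only calculation that supports wound-closure non-inferiority at 145; the other study's figure is 2164. Blood loss is third in the testing hierarchy (SAP 11.1.9) and must succeed before either autograft endpoint is tested, so a stated power of 58.8% affects what the trial can be expected to claim.

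**Working it through.** **1. The SAP's own figures reproduce.**
- Wound closure: D = 4 × 3.24²/1.36² = 22.7; n = 2 × 22.7/(0.62 + 0.73) = 33.6, so 34.
- Eschar removal: D = 4 × 3.24²/1.25² = 26.9; n = 2 × 26.9/(0.59 + 0.70) = 41.7, so 42.
- Blood loss: the SD is not printed. With a two-sided t-test (noncentral t), 58.8% power at 80 per arm and a difference of 465.54 implies SD ≈ 1341 ml. Power of 90% at 173 per arm and 468.47 implies SD ≈ 1340 ml. Sections 9.1.3 and 13.3 therefore share one SD.

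**2. Size of the earlier studies.** The analysed numbers are not printed, so they are backed out of 13.3.
- MW2010-03-02, autograft incidence: 3410/(3.2415 × 0.4988/0.2584)² = 87 evaluable; 87/0.58 = 150.
- MW2010-03-02, autograft area: 922/(3.2415 × 6.28/6.25)² = 87; again 150.
- MW2010-03-02, excision standard errors: 0.04 × 0.96/0.023² + 0.72 × 0.28/0.052² = 72.6 + 74.6 ≈ 147.
- MW2010-03-02, only printed size: 175 randomized.
- MW2004-11-02: the two autograft routes give 155, e.g. 720/(3.2415 × 0.40/0.476)² = 97 and 97/0.626 = 155. The excision standard errors give 158.

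The autograft sizes in 13.3 are thus reproduced by scaling the earlier standard error, N = N_prior × [(zα + zβ) × SE/target]².

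**3. Standard error implied by the event formula.**
- Wound closure: 150 × 0.675 ≈ 101 events; 2/√101 = 0.20, against 0.41 reported. Variance ratio about 4.2.
- Eschar removal: 155 × 0.645 ≈ 100 events; 2/√100 = 0.20, against 0.28 reported. Variance ratio about 2.0.

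**4. Wound closure by standard-error scaling (unrounded target 1.355).** N = N_prior × (3.24 × 0.41/1.355)², and power at 145 = Φ(1.355/[0.41 × √(N_prior/145)] − 1.96).

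| N_prior | N for 90% power | Power at 145 |
|---|---|---|
| 147 | 141 | 91% |
| 150 | 144 | 90% |
| 175 | 168 | 85% |

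The event formula itself would put power at 145 above 99.9%.

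The same scaling for MW2004-11-02 gives 155 × (3.24 × 0.63/0.18)² ≈ 20,000, against the printed 2164.

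**5. Eschar removal by the same scaling.** 155 × (3.24 × 0.28/1.25)² ≈ 82 (79 to 87 for N_prior 150 to 165). Power at 145 is about 99%.

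**6. Blood loss power (difference 465.54, SD 1341).**

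| Enrolled | Missing | Evaluable per arm | Power |
|---|---|---|---|
| 160 | 0% | 80 | 58.8% |
| 160 | 30% | 56 | 44.5% |
| 145 | 0% | 72.5 | 54.6% |
| 145 | 30% | 50.75 | 41.0% |

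**7. The 267.75.** √(129.52² + 240.98²) = 273.58, which matches the stated standard error and 9.1.3. Then −602.33 + 273.58/2 = −465.54. With SD 1341, 90% power needs 176 per arm, 352 evaluable, and 352/0.7 ≈ 503 enrolled.

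**The case against.** A reader might infer that 34, 42 and 58.8% contradict the inputs printed with them, or that the same inputs yield about 144, 82 and 41%. The documents do not support that. All three figures reproduce from the stated formulas. The 144 and 82 need a different variance method and study sizes that the SAP does not print. The 41% changes two things at once (160 to 145, and 30% missing), and the 30% rate stands in 13.3, not in 9.1.3.

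Further points on the SAP's side:
- The study size for MW2010-03-02 is uncertain. Rounding alone lets the NexoBrid arm in the excision route run from about 61 to 85. The autograft-incidence route needs a target of −0.2584, where the SAP prints −0.5078 as the result of −0.5078 + 0.4988/2. This is why a range is needed; the autograft-area route does not depend on that slip and also gives 150.
- The 0.41 is from a frailty model. The planned default is a marginal Cox model with sandwich variance, with frailty only if proportional hazards is rejected. Scaling 0.41 is therefore an approximation. It does not rescue the independent-events formula, which represents neither analysis.
- Wound closure is a safety endpoint outside the hierarchy, and the unfavourable 2164 is printed just before the 34.
- For blood loss, 9.1 sends the reader to 13.3 for the 145-patient calculations. There the 494 discloses low power on MW2004-11-02, while MW2010-03-02 needs only 80 enrolled. Section 13.3 also warns that power within the hierarchy will be lower than for each test alone. Missing values will be multiply imputed, so a flat 30% loss is pessimistic.

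These points limit the consequence. They do not make 34 a sound size for a clustered analysis, or 58.8% a description of the trial as enrolled.

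**Conclusion.** The point holds as one of method and consistency, not of failed arithmetic.

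- **Wound closure:** 34 understates the size at least fourfold. About 141 to 168 is the supportable range, with about 85 to 91% power at 145. It rests on a prior standard error from 147 to 175 patients, on similar information per patient in this trial, and on the frailty standard error approximating that of the marginal model. This does not show the endpoint to be underpowered on MW2010-03-02; it shows that the ample margin implied by 34 is not there.
- **Blood loss:** on MW2004-11-02 inputs, power at 145 is about 41 to 55%, depending on how much imputation recovers. The printed 58.8% lies above that range.
- **The 267.75:** an internal inconsistency with a small effect.
- **Eschar removal:** 42 is optimistic, but the conclusion stands, with about 99% power at 145 and 94 already reported by simulation. Nothing here casts doubt on the power for the primary endpoint.

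**What to change.** Text changes only, in SAP 13.3 and 9.1:

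1. In 13.3, replace the 34 (17 per group) for wound closure with about 141 to 168 patients and about 85 to 91% power at 145, stating the assumptions. The sponsor holds the analysed number from MW2010-03-02 and can replace the range with one figure. Apply the same scaling to the MW2004-11-02 estimate (2164 becomes about 20,000), so that one endpoint is not sized by two methods.
2. In 9.1.3, give blood-loss power at 145: about 55% with none missing and about 41% with 30% missing and no recovery from imputation (44.5% at 160 with 30% missing). Print the SD used.
3. In 13.3, replace 267.75 with 273.58, the anticipated difference with −465.54, and 346 and 494 with about 352 and 503.
4. For eschar removal, at most add a note that standard-error scaling gives about 82 and that power at 145 is unaffected in practice.

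No test, margin, endpoint or enrolment decision changes. The cost is that the stated support for stopping at 145 reads less favourably for wound closure and blood loss.
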